2. LIST OF ABBREVIATIONS

Term	Definition / description
AE	Adverse Event
ALT	Alanine Aminotransferase
AST	Aspartate Aminotransferase
BI	Boehringer Ingelheim
CI	Confidence Interval
CTR	Clinical Trial Report
DBL	Database Lock
eCRF	Electronic Case Report Form
FVC	Forced Vital Capacity
HRCT	High-Resolution Computer Tomography
ICH	International Conference on Harmonization
ILD	Interstitial Lung Disease
IPF	Idiopathic Pulmonary Fibrosis
MedDRA	Medical Dictionary for Regulatory Activities
SD	Standard Deviation
UIP	Usual Interstitial Pneumonia
TSAP	Trial Statistical Analysis Plan
ULN	Upper Limit of Normal

3. INTRODUCTION

As per ICH E9 ([9.1](#)), the purpose of this document is to provide a more technical and detailed elaboration of the principal features of the analysis described in the protocol, and to include detailed procedures for executing the statistical analysis of the primary and secondary variables and other data.

This TSAP assumes familiarity with the Clinical Trial Protocol (CTP), including Protocol Amendments. In particular, the TSAP is based on the planned analysis specification as written in CTP Section 7 “Statistical Methods and Determination of Sample Size”. Therefore, TSAP readers may consult the CTP for more background information on the study, e.g., on study objectives, study design and population, treatments, definition of measurements and variables, planning of sample size, randomization.

[figure not shown]
The objective of the current trial is to generate additional data on the efficacy of 150 mg bid nintedanib in Chinese patients with Chronic Fibrosing ILDs with a Progressive Phenotype compared to placebo over 52 weeks. The primary endpoint is defined in the same way as in the INBUILD trial (1199-0247). The efficacy of reduction in lung function decline will be measured by the annual rate of decline in FVC for nintedanib compared to placebo over 52 weeks.

Unless otherwise noted, SAS® Version 9.4 and R Version 4.0.1 (or higher) will be used for all analyses.

[figure not shown]
4. CHANGES IN THE PLANNED ANALYSIS OF THE STUDY

4.1 CLARIFICATION

- Comparing with the INBUILD trial (1199-0247), the duration of treatment of this study is only 52 weeks. The primary endpoint will include data collected up to last treatment visit, instead of day 373.
- The main analysis for primary efficacy endpoint of this study will be based on the treated set (according to randomized treatment), using all available data from baseline (excluded) up to week 52 visit. For patients who prematurely discontinued study treatment, data collected at follow-up visit and visits after treatment discontinuation will be included in the analysis.

- Due to the possible occurrence of mis-stratifications during the randomization process, the HRCT pattern as reported in the eCRF will be used in all analyses.
- Three patients were randomized by mistake, whose HRCT pattern was recorded incorrectly in the Interactive Response Technology (IRT) system. Two patients were randomized under “other HRCT fibrotic patterns” and the other one was randomized under “HRCT with UIP-like fibrotic pattern only”. They will be counted in the subpopulation of patients as collected in the eCRF in all analyses within the CTR.

[figure not shown]
5. ENDPOINTS(S)

5.1 PRIMARY ENDPOINT(S)

The primary efficacy endpoint is the annual rate of decline in Forced Vital Capacity (FVC) over 52 weeks expressed in mL. The analysis will be based on FVC values obtained at all post-baseline visits over 52 weeks. Handling of missing data is described in [Section 6.6](#).

5.2 SECONDARY ENDPOINT(S)

Not applicable since there is no secondary endpoint.

[figure not shown]

**Boehringer Ingelheim
TRIAL STATISTICAL ANALYSIS PLAN
1199-0434**

Page 9 of 33

c40328414-01

Proprietary confidential information © 2025 Boehringer Ingelheim International GmbH or one or more of its affiliated companies.

6. GENERAL ANALYSIS DEFINITIONS

6.1 TREATMENT(S)

For the definition of treatment administered during the trial, see Section 4 of CTP.

- Screening: From informed consent to randomization
- Treatment period: From first trial drug intake to last trial drug intake
- Residual effect period / Safety follow-up: From the last trial drug intake plus 1 day to last trial drug intake plus 7 days
- Off-treatment period: From start date of trial drug interruption to re-start of trial drug

All analyses will be based on the planned treatment groups (Nintedanib 150 mg bid vs. Placebo) as randomized by IRT. The subjects will be analyzed according to the stratum to which they actually belong to, regardless of any stratification error at randomization.

6.2 IMPORTANT PROTOCOL DEVIATIONS

Potentially important protocol deviations (iPDs) will be handled according to BI standards ([9.5](#)). The number and proportion of patients with iPDs will be presented for completeness purposes and to demonstrate the adherence to the CTP. Handling of iPDs in analysis is included in the DV domain specifications and stored within the TMF.

6.3 INTERCURRENT EVENTS

Intercurrent events and handling strategies with respect to the primary efficacy endpoint are described in [Table 6.3:1](#).

For the main analysis, intercurrent events such as premature treatment discontinuation and restricted medication use will be handled by applying treatment policy strategy, i.e., all available data collected up to week 52 visit will be included in the analysis.

Death will be handled by applying while-alive strategy, i.e., data collected while patient is alive will be included in analysis.

The use of Pirfenidone and Nintedanib (non-IMP prescribed by investigator) are prohibited during the trial and considered as important protocol violations. In the supplementary analysis, prohibited medication and restricted medication will be handled by applying while-on-treatment strategy, i.e., data collected after the initiation of prohibited or restricted medication will not be included in the analysis.

Further details of intercurrent event handling strategies will be described in [Section 7](#).

Table 6.3: 1 Intercurrent events and handling strategies

Intercurrent event	Main analysis strategy	Supplementary strategy
Treatment discontinuation	Treatment policy	While-on-treatment
Initiation of restricted medication	Treatment policy	While-on-treatment
Initiation of prohibited medication	Treatment policy	While-on-treatment
Death	While-alive	While-alive

6.4 SUBJECT SETS ANALYSED

Patient sets analyzed are defined as:

- Screened set (SCS):
This subject set includes all subjects who signed informed consent.
- Randomized set (RS):
This subject set includes all randomized subjects, whether treated or not.
- Treated set (TS):
This subject set includes all subjects who were dispensed study medication and were documented to have taken at least one dose of investigational treatment.

Table 6.4: 1 Subject sets analyzed

Class of analysis	Subject set		
	Screened set	Randomized set	Treated set
Primary endpoint			X
Further endpoint			X
Safety and treatment exposure			X
Demographic & baseline characteristics			X
Disposition		X	
Reason for non-randomization	X		

6.5 SUBGROUPS

Subgroup analysis is not planned.

6.6 HANDLING OF MISSING DATA AND OUTLIERS

In general, missing data will not be imputed. Exceptions and further details will be described in [Section 7](#).

For continuous efficacy endpoints, missing data will be handled by the Random Slope and Intercept (RSI) model and Mixed Models for Repeated Measures (MMRM), assuming a missing at random mechanism.

[figure not shown]
For binary endpoints, missing data will be considered as worst-case outcome in the main analysis, e.g., no response.

Missing or incomplete AE and CM dates are imputed according to BI standards ([9.2](#)).

6.7 BASELINE, TIME WINDOWS AND CALCULATED VISITS

As a general rule, the last assessment / measurement observed prior to the start of trial medication will be assigned to baseline. Note that for some trial procedures (e.g., body weight, vital signs, laboratory tests), this may be the value measured on the same day as trial medication started. In these cases, it will be assumed that the measurements were taken prior to the intake of any study medication (if the measurement time was not captured). If no further data available, this can also be the last screening assessment.

Visit windowing will be performed as described in [Table 6.7: 1](#), [Table 6.7: 2](#) and [Table 6.7: 3](#). In order to assign data to the relevant study visit based on the actual day of the assessment, data will be analysed using the re-calculated visits in statistical tables. However, in listings, all visits performed will be displayed (even if outside time-window), along with the re-calculated visit.

If after windowing of visits at baseline, the last value prior to first drug intake will be taken into account. If after windowing of post-baseline visits, two or more visits fall in the same interval, then the measurement closest to the planned visit will be taken into account. In case two measurements are equidistant from the planned visit, then the last one will be used in analysis.

7. PLANNED ANALYSIS

The labelling and display format of statistical parameters will follow BI standards (9.3). For End-Of-Text tables, the set of summary statistics are: N / Mean / SD / Min / Median / Max. In case extreme data outside of the expected range are observed, quartiles and percentiles will be presented additionally.

Tabulations of frequencies for categorical data will include all categories depicted in the eCRF and will display the number of observations in a category as well as the percentage (%) relative to the respective treatment group (unless otherwise specified, all patients in the respective patient set whether they have non-missing values or not). The category missing will be displayed only if there are actually missing values.

Unless otherwise noted, all analyses will be conducted on the treated set (TS).

7.1 DEMOGRAPHIC AND OTHER BASELINE CHARACTERISTICS

Descriptive statistics will be provided for disposition, demographics, baseline disease characteristics, presented by treatment groups and overall total.

Disposition table will include the number of patients randomized and treated. The number and percentage of patients who completed and prematurely discontinued study treatment will be summarized by treatment groups, the reasons for treatment discontinuation will be shown. Similarly, the number and percentage of patients who completed and prematurely discontinued observation period will also be summarized by treatment groups, the reason for study discontinuation will be shown. Where percentages are shown, the denominator will be the number of patients treated in each treatment group.

In addition, the reason for non-randomization will be summarized based on the screened set.

Demographics such as Age, Sex, Race, Ethnicity, Weight (kg), Height (cm) and BMI will be summarized by treatment groups.

Trial indication characteristics including original underlying ILD diagnoses and baseline disease extent as collected in eCRF will be summarized by treatment group. In addition, the underlying ILD diagnosis grouping will be summarized by treatment group, the grouping will be determined by medical review and documented prior to DBL.

7.2 CONCOMITANT DISEASES AND MEDICATION

Concomitant diseases and concomitant medications will be descriptively summarized by treatment groups and overall total.

Concomitant diseases will be coded according to the most recent version of MedDRA. Concomitant medications will be coded according to the most recent version of the World Health Organization – Drug Dictionary (WHO-DD).

A medication will be considered concomitant to treatment if it:

- is ongoing at the start of trial medication intake.

- starts within the treatment period (see [Section 6.1](#) for a definition of study phases).

Concomitant medication use will be summarized with frequency and percentage of subjects by ATC3 class and preferred name, grouped by randomized treatment.

On-treatment restricted medication and prohibited medication will be summarized by treatment groups, definitions of restricted and prohibited medications are depicted in CTP Section 4.2.2., prohibited medication will be documented in the iPD specification.

7.3 TREATMENT COMPLIANCE

The overall compliance (%) will be summarized by treatment groups and overall total. If the number of capsules actually taken is missing for an expected visit, the overall compliance is not calculated.

Compliance will be calculated over 52 weeks as:

$$\text{Compliance [%]} = \frac{\text{Number of capsules actually taken}}{\text{Number of capsules should have been taken}} \times 100$$

The number of capsules which should have been taken over the 52-week treatment period will be calculated as:

Number of capsules = (date of last drug intake – date of first drug intake + 1) × 2

In case of dose reduction to 100 mg bid, the calculation of compliance remains the same. The duration of treatment interruptions due to AE will be subtracted from the studied treatment duration when calculating number of capsules should have been taken.

Compliance will be categorised into classes: <50%, ≥50% - <80%, ≥80% - ≤ 120%, > 120%. Compliance category will be summarized by treatment groups and overall total.

7.4 PRIMARY OBJECTIVE ANALYSIS

7.4.1 Main analysis

The primary efficacy endpoint is the annual rate of decline in Forced Vital Capacity (FVC; expressed in mL) over 52 weeks. The main analysis will be based on the TS (according to randomized treatment), using all available data from baseline (excluded) up to week 52 visit. For patients who prematurely discontinued study treatment, data collected at follow-up visit and visits after treatment discontinuation will be included in the analysis. For patients who had multiple FVC measurements on the same day, the last measurement will be used in the analysis. Intercurrent event handling strategies for main analysis are described in [Section 6.3](#).

The main analysis uses a restricted maximum likelihood (REML) based approach with a random slope and intercept model. The analysis will include the fixed, categorical effects of treatment, HRCT pattern at baseline, fixed continuous effects of time and baseline FVC as well as the treatment-by-time and baseline-by-time interactions. Random effects will be included for patient response for both time and intercept. The HRCT pattern at baseline collected in eCRF will be used in the analysis.

The statistical model can be written as follows:

$$y_{ijkm} = (a_i + \vartheta_m + \beta_0 S_i + \tau_k) + (g_i + \beta_s S_i + \varphi_k) t_{ij} + e_{ij}$$

$$\begin{aligned}(a_i, g_i) &\sim N_2 (\mathbf{0}, \Sigma) \\ &\text{iid} \\ e_{ij} &\sim N (0, \sigma^2)\end{aligned}$$

The components of the model are as follows:

y_{ijkm} = FVC for patient i with HRCT pattern m at time j receiving treatment k
 a_i = random intercept effect for patient i, $i=1,2,\dots$
 ϑ_m = intercept coefficient of HRCT pattern m, $m=1,2$. (“other HRCT fibrotic patterns” as the class reference)
 β_0 = intercept coefficient of baseline FVC
 S_i = baseline FVC measurement for patient i
 τ_k = intercept coefficient of the effect of treatment k, $k=1,2$
 g_i = random slope effect for patient i
 β_s = slope coefficient of baseline FVC
 φ_k = slope coefficient of the effect of treatment k
 t_{ij} = time of measurement j for patient i, $j= 1,2,\dots J_i$
 e_{ij} = the random error associated with the time j of patient i. Measurement errors are independent and normally distributed with mean 0 and variance σ^2 , and uncorrelated with a_i and g_i .
 Σ = a 2x2 unstructured covariance matrix

Within patient errors are assumed to follow a random coefficient regression model with random effect for intercept and slope. An unstructured variance-covariance structure will be used to model these random slope and intercept. The Kenward-Roger approximation will be used to estimate denominator degrees of freedom and adjust standard errors.

In case of model non-convergence, methods to overcome the issue are described in [Section 10.1](#). The first model to converge will be used as the main analysis on the primary endpoint.

The point estimate of treatment difference between the nintedanib and placebo group as well as two-sided 95% CI will be provided. No formal statistical testing will be performed. The primary treatment comparison of slopes will be assessed through the treatment-by-time interaction coefficient.

[figure not shown]
SAS code specifications are included in [Section 10.2](#).

**Boehringer Ingelheim
TRIAL STATISTICAL ANALYSIS PLAN
1199-0434**

Page 17 of 33

c40328414-01

Proprietary confidential information © 2025 Boehringer Ingelheim International GmbH or one or more of its affiliated companies.

**Boehringer Ingelheim
TRIAL STATISTICAL ANALYSIS PLAN
1199-0434**

Page 18 of 33

c40328414-01

Proprietary confidential information © 2025 Boehringer Ingelheim International GmbH or one or more of its affiliated companies.

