5. ASSESSMENTS

5.1 ASSESSMENT OF EFFICACY

5.1.1 FVC

Spirometry measurements will be performed according to ATS/ERS 2005 guideline ([P05-12782](#)). FVC will be assessed using standardised spirometry equipment which will be provided centrally with supplies of pre-calibrated disposable flow sensors. These sensors demonstrate variability within the required standards of +/-3% determined by the American Thoracic Society (ATS)/European Respiratory Society (ERS) [[P05-12782](#)]. As such there is no need to conduct daily calibration prior to use. Only these spirometers are to be used for this trial. Spirometry performance will be centrally reviewed. Spirometry will be conducted while the patient is in a seated position. The test will be done in triplicate (three curves to be provided), and the best result selected according to the guidelines. The best of three efforts will be defined as the highest FVC, obtained on any of the three blows meeting the ATS/ERS criteria with preferably a maximum of five manoeuvres.

Efforts should be made, to schedule the spirometric measurements at approximately the same time of the day, with reference to baseline measurement (Visit 2). On days of clinic visits, patients must refrain from strenuous activity at least 12 hours prior to pulmonary function testing. Smoking should be discouraged throughout the visit days (clinic visit) and will not be permitted in the 30-minute period prior to spirometry. Patients should also avoid cold temperatures, environmental smoke, dust, or areas with strong odours (e.g. perfumes). If treated with bronchodilators, wash-out of 24 hours for long acting and 8 hours for short acting bronchodilators should be observed before spirometry. Spirometry results will be electronically transmitted. To ensure the quality of primary endpoint measurement a central spirometry review is put in place to provide feedback to the investigational site and the CRA on the quality of the data received from the site.

Further instructions regarding FVC measurements will be provided in the ISF.

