6.2.4 Dose reduction visit / dose increase visit

If a patient experiences a drug related adverse event, the dose can be reduced and the dose can be re-increased after recovery as described in [Section 4.2.1](#). In both cases, the patient will have to come back to a visit where the following will be performed:

- Physical examination including vital signs.
- Adverse events and concomitant therapy will be assessment since last visit.

Proprietary confidential information © 2025 Boehringer Ingelheim International GmbH or one or more of its affiliated companies

- Local dipstick pregnancy test (if applicable).
- Safety blood and urine samples will be collected and submitted to the central laboratory.
- Spirometry (FVC) in the allowed time window will be performed.
- Trial medication will be collected and treatment compliance will be reviewed.
- IRT registration for reduction or increase of the dose and trial medication dispensation.

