7.1 NULL AND ALTERNATIVE HYPOTHESES

No formal hypothesis is tested.

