7.2.2 Primary endpoint analyses

The primary endpoint is the annual rate of decline in FVC [mL] over 52 weeks. The primary analysis will be based on all randomized patients who received at least one dose of trial medication, using all available data from baseline (excluded) up to Week 52, including visits done after premature treatment discontinuation, EOT visits and follow-up visits done before Week 52 (i.e. including all measurements after first drug intake and before or on day 373). The primary analysis will use a restricted maximum likelihood (REML)-based approach with a random slope and intercept model. The analysis includes fixed effects for treatment, HRCT pattern, and baseline FVC [mL], as well as the treatment-by-time and baseline-by-time interactions. Random effects will be included for the patient response for both time and intercept. Baseline FVC in mL will be included as a covariate in the analysis model. Baseline FVC is defined as the FVC result recorded at Visit 2, unless missing in which case the screening result will be used. The HRCT pattern (“UIP-like fibrotic pattern” or “Other fibrotic patterns”) will also be used as a covariate for the analysis performed. The point estimate of treatment difference between the nintedanib and placebo group will be provided as well as 95%CI. No statistical testing will be performed.

A sensitivity analysis including only on-treatment measurements of FVC (ml) will be presented. The same model as for the primary analysis will be used. This model implies that data are assumed to be missing at random (MAR) and it is implicitly supposed that patients who dropout would have behaved similarly to those who remained in the study.

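### Does the SAP's rule of using the last same-day FVC replace the protocol's best-of-three measurement in the primary analysis?

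*SAP*

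**What the plan says.** Protocol 5.1.1 describes a single spirometry test: "The test will be done in triplicate (three curves to be provided), and the best result selected according to the guidelines". It then defines best: "The best of three efforts will be defined as the highest FVC, obtained on any of the three blows meeting the ATS/ERS criteria". The same section sets up a central spirometry review that reports data quality back to the site and the CRA.

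SAP 7.4.1, where it lists the data entering the main analysis, adds: "For patients who had multiple FVC measurements on the same day, the last measurement will be used in the analysis".

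Elsewhere both documents treat FVC as one value per visit:

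- SAP 5.1: "The analysis will be based on FVC values obtained at all post-baseline visits over 52 weeks".
- SAP 6.7, on post-baseline windowing, applies when "two or more visits fall in the same interval, then the measurement closest to the planned visit will be taken into account"; if two are equally close, the later one is used.
- Protocol 7.2.2: "Baseline FVC is defined as the FVC result recorded at Visit 2, unless missing in which case the screening result will be used".

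The protocol has no rule for two complete tests on one day. Extra tests can occur, because Protocol 6.2.4 requires spirometry at dose-change visits ("Spirometry (FVC) in the allowed time window will be performed"). It does not say whether such a visit may share a day with a scheduled one.

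The trial only estimates. Protocol 7.1 says "No formal hypothesis is tested", and the result is a difference in slopes with a 95% CI.

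**The concern.** FVC depends on effort, and a poor effort can only lower the reading. That is why the protocol takes the highest acceptable blow. Beside it, a rule that takes the last value regardless of quality looks like a different and worse measurement. If last meant the third blow, the analysed FVC would be lower and more variable than the protocol intends. If it meant the last of two tests, a weak repeat could displace a good result. SAP Section 4, which lists clarifications to the planned analysis, does not mention the rule.

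The primary endpoint is at stake in a small trial, with about 30 placebo patients. Week 52 has the most leverage on each patient's slope. A shift confined to Week 52 could move a single patient's slope by tens of mL/year, against a planning effect of 107 mL/year.

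**Working it through.** **1. Which level does each rule act on?** Every test consists of three blows. If a measurement in SAP 7.4.1 were a blow, every patient would have several at every visit. The sentence is worded for an exception, for those patients who had more than one. SAP 5.1, SAP 6.7 and Protocol 7.2.2 all use one value per visit, and the model in SAP 7.4.1 indexes a single FVC per patient and time point. The consistent reading is that Protocol 5.1.1 turns three blows into one result, and SAP 7.4.1 then chooses between results if a day has more than one. The two rules apply in sequence and do not conflict.

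**2. The plan's own precision.** Inputs from Protocol 7.5: SE of the INBUILD difference 21.15, arms of 331 and 332, planned arms of 60 and 30, effect 107 mL/year.

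- Implied SD of a patient's slope = 21.15 / √(1/331 + 1/332) = 272.3.
- SE for 60 vs 30 = 272.3 × √(1/60 + 1/30) = 60.9.
- P(estimate ≥ 53.5) = Φ(53.5/60.9) = 81.0%; for 42.8 and 32.1 it is 85.4% and 89.1%. The protocol states 81.7%, 86.0% and 89.6%, so its figures are reproduced to within one point.

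**3. Two tests on one day (the consistent reading).** The documents give no between-test SD; 50 mL is assumed (range 30–100).

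- If the two tests are exchangeable, the last has the same mean and variance as any single test. Its shift relative to visits without a repeat is 0.
- The higher of two has expectation +0.564 SD, that is 0.564 × 50 = 28 mL (17–56), at repeat visits only.

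The visit-specific shift therefore comes from taking the highest, not from taking the last. To compare precision, assume 2–10% of visits have a second test and a between-test SD of 50–150 mL. Taking the last rather than the higher then leaves the SE at 60.9–61.3 and the 53.5 mL probability at 80.9–81.0%.

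**4. Last blow instead of best blow (the literal reading).** For the highest of three normal efforts, the mean is +0.846 SD and the variance 0.560 SD². With visits at weeks 2, 4, 6, 12, 24, 36 and 52, Sxx = 0.789 yr². The extra slope variance is w²(1 − 0.560)/0.789, where w is the assumed blow SD. At w = 50 this is 1,394, so the slope SD is √(272.3² + 1,394) = 274.8 and the SE is 274.8 × √0.05 = 61.5.

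| Blow SD w (mL, assumed) | Level shift (mL) | SE of difference | P(estimate ≥ 53.5) |
|---|---|---|---|
| best of three | 0 | 60.9 | 81.0% |
| 30 | −25 | 61.1 | 80.9% |
| 50 | −42 | 61.5 | 80.8% |
| 100 | −85 | 63.1 | 80.2% |
| 150 | −127 | 65.9 | 79.2% |

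The level shift is the same at every visit and in both arms, so it goes into the intercept. Simulated slope differences for a true 107 were 106.5–107.2 with the last blow and 106.6–107.6 with the best, over w of 50–150 mL. With 2,000 replicates and an SE near 60, simulation error is about 60/√2,000 = 1.3, so the two cannot be told apart.

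**5. A shift at Week 52 only.** Week 52 lies 0.626 years above the mean visit time, so a shift there enters a patient's least-squares slope at 0.626/0.789 = 0.79 per year. A 42 mL shift gives about −34 mL/year and a 28 mL shift about −22. The −34 cannot be combined with the blow reading, which affects all visits. As arm effects, one affected placebo patient in 30 moves the arm mean by 34/30 = 1.1 or 22/30 = 0.7 mL/year. Three such patients move it by 3.4 or 2.2. The SE of the difference is about 61.

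**The case for a change.** The strongest case against the rule is that it selects by order and ignores quality. A lower or technically poorer repeat would displace a better test, which departs from the spirit of Protocol 5.1.1. Repeats are plausible, because central review comments on test quality and dose-change visits carry their own spirometry. Those visits follow drug-related adverse events, so extra tests may be more frequent on nintedanib. The term measurement is not defined in SAP 7.4.1, and neither document says which of two same-day baseline tests counts in so many words.

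The undefined term and the absent quality condition stand as gaps in detail. The rest carries less weight. A repeat made because the first test was poor may well be the better of the two. Imbalance between arms does not bias the last-value rule when tests are exchangeable, but it would bias a highest-value rule in favour of the arm with more repeats. For baseline, the general rule in SAP 6.7 already takes the last assessment before first drug intake, which matches the post-baseline rule. Protocol 5.1.1 describes central review as quality feedback and does not say that it accepts or rejects individual values, so a rule based on central acceptance would presume a step the documents do not describe. Silence in SAP Section 4 is no omission: the protocol had no same-day rule to change, and SAP Section 3 gives the SAP the task of adding technical detail.

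**Conclusion.** The concern does not hold. The documents do not show that the analysed FVC departs from the protocol's best-of-three result. On the consistent reading, the last same-day value is itself a best-of-three and is neither lower nor noisier than values at visits with one test. This assumes that same-day tests are exchangeable. On the literal blow reading the slope difference remains unbiased, and the SE rises from 60.9 to 61.1–63.1 mL/year for a blow SD of 30–100 mL.

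Blow SD, between-test SD and the frequency of same-day repeats are assumptions, since the documents give none of them. The SAS code in SAP 10.2 was not available for this check and may define the term further. What is left is an undefined word in a tie-break and a choice between last and highest on which reasonable statisticians differ. Neither calls for a change to the plan.
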